## **15.0 STATISTICAL CONSIDERATIONS**

### **15.1 Sample Size Justification**

This sample size has been determined by the primary endpoint of microparticle released at 6 months with an adjustment to the alpha level to account for the fact there are five primary endpoints. From Figure 1, the mean (standard deviation) of number of microparticles released is 140,000 (75,000) and it is anticipated that treatment with imatinib will decrease that amount at least 50% to 70,000. A two-sided paired t-test with alpha level  $0.05/5 = 0.01$  will have 89% power to detect this difference when the sample size is 20 subjects (assuming the pre/post treatment correlation is 0.5). We estimate a sample size of 20 patients total (10 patients from each site) would be feasible to recruit and would meet these statistical criteria to provide adequate data to assess effect.

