## 4.0 STUDY OBJECTIVES

### 4.1 Primary Aims

- 4.11 To examine the biochemical effects of imatinib by:
  - a. quantitation of band 3 phosphorylation and microparticle release from sickle RBCs
  - b. functional RBC analysis

As noted in Figure 2, we expect band 3 tyrosine phosphorylation to decrease dramatically in patients treated with imatinib. We also anticipate a reduction in the numbers of RBC-derived microparticles in circulation (quantitated by assaying the number of glycophorin A positive microparticles in peripheral blood samples by flow cytometry; see Figure 3B). We will evaluate for improvement in the red cell cytoskeleton mechanics by ektacytometry (which should improve due to reduced loss of RBC membrane as a consequence of decreased band 3 phosphorylation), oxygenscan, and determination of percent irreversibly sickled cells.

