### 4.3. Endpoints

- 4.31 Primary Endpoints:
  - a. Biochemical Effects to RBCs (see Section 17)
    - i. Band 3 Phosphorylation
    - ii. Microparticle Release
  - b. Functional RBC analysis (see Section 17)
    - i. Percent Irreversibly Sickled Cells at Month 6
    - ii. Ektacytometry
    - iii. OxygenScan to evaluate for altered susceptibility to sickling
- 4.32 Secondary Endpoints:
  - a. Clinical Outcomes

- i. Vaso-occlusive Crisis (VOC)
  - i. Defined as an acute episode of pain lasting greater than 24 hours, with no medically determined cause other than a vaso-occlusive event that resulted in treatment with oral or parenteral opiate agents and/or parenteral nonsteroidal anti-inflammatory agents.
  - ii. To be documented in pain diary by patient/guardian and reviewed at each visit
  - iii. Measured by pain scale (1-10) or Wong-Baker Faces scale based on age:
- ii. Acute Chest Syndrome
  - i. Defined as respiratory distress (hypoxia, shortness of breath, chest pain, tachypnea) with evidence of an infiltrate on chest x-ray
  - ii. Will be reviewed at each visit, as well as extracted from the EMR by each site
- iii. Opioid Use
  - i. Defined as both oral and parenteral opioid use
  - ii. Oral use will be documented in pain diary by patient/guardian and reviewed at each visit.
  - iii. Frequency of refills and parenteral opioid use will be extracted from the EMR by each site
- iv. Hospitalizations
  - i. Defined as an emergency room or clinic visit resulting in an inpatient admission or observation for a sickle cell-related event (e.g. vaso-occlusive pain, acute chest syndrome, etc).
  - ii. Will be reviewed at each visit, as well as extracted from the EMR by each site
- v. Assessment of tolerability and evaluation for any toxicities of imatinib in patients withSCA

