## 15.4 Efficacy evaluation

Descriptive statistics will be calculated for all endpoints before, during, and after treatment. Changes before and 6 months after treatment in biochemical endpoints will be tested with two-sided paired t-tests. This analysis will be supplemented with single group repeated measures ANOVA to test for effects over time since there are 3 measures on treatment. Many secondary endpoints are counts (e.g. frequency of refills of opioids, number of hospitalizations). Depending on the distributions of these outcomes, we will either: 1) dichotomize and compare with McNemar's test; 2) treat as ordinal and compare with a Cochran-Mantel-Hazensel type test; or 3) treat as continuous and conduct either paired t-test or Wilcoxon signed rank tests. Since the pain measure will depend on age, we will only statistically analyze when there are at least 6 participants using a single-group repeated measures ANOVA model. Otherwise, only graphical descriptions will be used.

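### Section 15.4 states no significance level for the five primary endpoints; Holm at 0.05 would beat the equal 0.01 split of Section 15.1 at no cost in patients

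*Combined protocol and SAP*

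**What the plan says.** Section 4.31 lists five primary endpoints: band 3 phosphorylation and microparticle release under a biochemical heading; percent irreversibly sickled cells at Month 6, ektacytometry and OxygenScan under a functional heading.

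Section 15.1 powers the study on microparticles, "with an adjustment to the alpha level to account for the fact there are five primary endpoints". It divides 0.05 by 5 and quotes 89% power at 0.01 with 20 patients. This is the only place where a level for the efficacy tests appears.

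Section 15.4 says: "Changes before and 6 months after treatment in biochemical endpoints will be tested with two-sided paired t-tests". It adds a single-group repeated measures ANOVA as a supplement. It gives no level, does not refer back to 0.01, and names no multiplicity procedure. No other section supplies one.

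**The concern.** Two things are unsatisfactory.

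First, the rule that protects the family of five sits only in a sample size calculation for one endpoint. An analyst working from 15.4 could test each endpoint at 0.05 and still comply with its wording.

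Second, where the plan does show its rule, it is a fixed 0.01 per endpoint. A step-down rule gives the same protection and loses nothing. It gains when more than one endpoint truly changes, and the plan expects that. On band 3, Section 4.1 says "we expect band 3 tyrosine phosphorylation to decrease dramatically in patients treated with imatinib". It also anticipates fewer microparticles, and on function it says "We will evaluate for improvement in the red cell cytoskeleton mechanics by ektacytometry". Power is given for microparticles alone, so nothing is known about the chance of detecting the other four at 0.01.

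**Working it through.** **Which endpoints 15.4 covers.** Section 4.31 uses the biochemical label for two of the five. Section 4.1, however, introduces the aim as "To examine the biochemical effects of imatinib by" and places functional red cell analysis beneath it. Section 15.1 counts five endpoints, and 15.4 moves straight on to "Many secondary endpoints are counts". The best reading is that the paired t-tests cover all five, but it is a reading.

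**Reproducing the plan's power.** Inputs from 15.1: baseline mean 140,000, SD 75,000, fall of 70,000, pre/post correlation 0.5, n = 20, two-sided 0.01.

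- SD of the difference, taking equal SDs before and after: 75,000 × √(2 × (1 − 0.5)) = 75,000.
- Standardised effect: d = 70,000/75,000 = 0.933.
- Noncentrality: 0.933 × √20 = 4.17, with 19 degrees of freedom.
- Exact power from the noncentral t: 88.98%, against the stated 89%.

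**Family-wise error.**

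- 0.01 each: at most 5 × 0.01 = 0.05; 1 − 0.99⁵ = 4.90% if the endpoints are independent.
- 0.05 each, a possible reading of 15.4: 1 − 0.95⁵ = 22.6% if independent. In simulation it was about 17% at a correlation of 0.6.
- Holm: at most 5% under any dependence. Simulated rates were at or below 5% within simulation error.

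**What Holm does.** It compares the ordered p-values with 0.05/5, 0.05/4, 0.05/3, 0.05/2 and 0.05, and stops at the first failure. The first step is the plan's 0.01, so no rejection under the 0.01 rule can be lost. Microparticle power at each threshold is:

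| Threshold | 0.01 | 0.0125 | 0.0167 | 0.025 | 0.05 |
|---|---|---|---|---|---|
| Power | 89.0% | 90.7% | 92.7% | 95.0% | 97.7% |

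**Size of the gain.** The documents give no effect sizes for the other four endpoints and no correlation between endpoints, so both are assumed over a range. I simulated 100,000 trials per scenario with n = 20, five equally correlated normal paired differences, and microparticles at d = 0.933. The Monte Carlo standard error is at most √(0.25/100,000) = 0.16 point. With all four other endpoints changing by d, for correlations 0 / 0.5 / 0.8:

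| d of the other four | Power of each at 0.01 | Power of each with Holm | Gain for microparticles (points) |
|---|---|---|---|
| 0.3 | 9% | 11 / 12 / 13% | 0.7 / 0.2 / 0.0 |
| 0.5 | 30% | 39 / 40 / 40% | 2.5 / 0.8 / 0.0 |
| 0.7 | 61% | 77 / 75 / 73% | 5.6 / 3.0 / 0.9 |
| 0.933 | 89% | 97 / 96 / 94% | 8.1 / 6.7 / 5.2 |

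With the other four at d = 0.7, the mean number of endpoints detected rises from 3.3 to between 3.8 and 4.0. With all five at 0.933, the chance of showing all five rises from 56-76% to 88-92%.

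The gain is small when few endpoints change. If one other endpoint changes, its power goes from 30% to 33% at d = 0.5, or from 61% to 64% at d = 0.7. If only microparticles change, their power rises by about 0.1 point.

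**The case against.** The equal split is a legitimate choice, and its divisor matches the endpoint list. In an open-label pilot meant to inform a later trial, declaring a fourth or fifth biomarker significant matters less than in a confirmatory study. The real gap is the silence of 15.4, and writing 0.01 there would close it without Holm. The benefit of Holm also rests on assumed effects. Weak endpoints stay weak (11-40% power at d of 0.3 to 0.5), and a dramatic effect needs no help: at an assumed d of 1.2, power at 0.01 is already 98.9%. Holm also has no simple matching simultaneous confidence intervals, and a pilot may value intervals more than extra rejections.

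Much of this stands. The split is not an error, and restating 0.01 would meet the minimum need. The gains are conditional, and some are small. But 15.4 needs a sentence in any case, and of two rules that cost the same and control the same error, one never does worse. The interval point is a real but limited drawback: 99% intervals can still be reported, although they may disagree with Holm rejections after the first step.

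It is also fair to say that Holm needs one p-value per endpoint, and that Section 4.31 names no single parameter for ektacytometry or OxygenScan. The lab manual cited in Section 17 may do so. The 0.01 rule has the same need.

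**Conclusion.** The concern holds. The analysis section carries no level or multiplicity rule, and the rule implied by the sample size section is valid but can be improved at almost no cost. The change is advisable, not a correction of a false result.

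The sample size of 20 is unaffected, and 89% stands as a minimum for microparticles under the assumptions of 15.1. For each of the other four endpoints, the gain ranges from about 2 to 16 points when all four change by between 0.3 and 0.933 SD. It is about 3 points when only one of them changes by 0.5 or 0.7 SD. That Holm keeps the error at 5% and loses no rejection does not depend on these assumptions; only the size of the gain does.

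**What to change.** Add to Section 15.4:

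> Each of the five primary endpoints in Section 4.31 will be tested for change from baseline to Month 6 with a two-sided paired t-test. Family-wise error will be controlled at two-sided 0.05 by Holm's step-down procedure: ordered p-values are compared with 0.01, 0.0125, 0.0167, 0.025 and 0.05, stopping at the first non-rejection. The repeated measures ANOVA is supportive.

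Name one parameter each for ektacytometry and OxygenScan, or point to where the lab manual does so, so that the family contains exactly five p-values. In 15.1, keep 89% and describe it as the minimum power for microparticles.

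The cost is this short addition to the text, made before the data are analysed. No patients, visits or assays are added. If 99% intervals are reported, note that they may not agree with every Holm decision.

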### **15.2 Safety evaluation**

The assessment of safety will be based mainly on the frequency of adverse events, particularly adverse events leading to discontinuation of treatment and on the number of significant laboratory abnormalities.

Adverse events will be summarized by presenting the number and percentage (as appropriate) of patients having any adverse event by body system, type of adverse event, and maximum severity according to CTCAE grade. Those adverse events which result in death, discontinuation or are otherwise classified as dose limiting will be presented separately.

Laboratory data will be summarized using the NCI CTCAE version 4.03 criteria.

### **15.3 Safety Monitoring**

DLTs (see Section 8 for definition) will be continuously monitored. If the stopping rule is met, enrollment will be halted, and a data safety meeting will be convened to determine whether or not the study should be continued. Sequential boundaries will be used to monitor dose-limiting toxicity rate. The accrual will be halted if excessive numbers of dose-limiting toxicities are seen, that is, if the number of dose-limiting toxicities is equal to or exceeds  $b_n$  out of  $n$  patients with full follow-up (see table below). This is a Pocock-type stopping boundary that yields the probability of crossing the boundary at most [probability of early stopping] when the rate of dose-limiting toxicity is equal to the acceptable rate [event probability  $\theta$ ].

Number of Patients, $n$	1	2	3	4	5	6	7	8	9	10	11	12	13	14	15	16	17	18	19	20
Boundary, $b_n$	-	-	3	4	4	4	5	5	6	6	6	7	7	7	8	8	8	9	9	

This boundary is equivalent to testing the null hypothesis, after each patient, that the DLT rate is equal to 0.2, using a one-sided level 0.021430 test.

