## **6.0 TREATMENT PROGRAM**

All patients with sickle cell anemia will be treated in the same group. There will not be a randomization.

Patients will receive Imatinib orally once daily for 6 months.

The starting dose for subjects will be 340 mg/m^2/day with a maximum dose of 600 mg daily. Drug doses will be rounded to nearest 50 mg according to the dosing table in Appendix A. Dosing should be based on the body surface area (BSA) obtained at each clinic appointment. Drug will be dispensed as a 30-day supply at each visit. Patients will be asked to bring the prescription bottle with them to each visit to assist with monitoring compliance.

Clinic visits will occur at initiation of imatinib and then every 30 days +/- 7 days. Monthly visits will consist of interim history, assessing for adverse side effects and compliance. Participants will be asked to have blood drawn (see Section 11) 2 weeks +/- 3 days after initiation of the drug. Additionally, during the first two months of drug administration, patients will be called or texted a survey link weekly for follow-up safety assessments, except for the participant's in-clinic visits at week 2, 4 and 8. The survey link will come via an app, called Twilio, that allows REDCap the capability to send SMS text messages to survey respondents. If the patient is unable to be reached by phone for at least 3 of the 4 weekly assessments each month, they will be asked to be seen in clinic for a safety assessment. If the patient is unable to do so, they will be removed from protocol therapy for protocol non-compliance. The 1 month, 3 month, 6 month, and 1-month off-therapy visits will consist of a comprehensive history and physical

exam, as well as laboratory and diagnostic studies documented in Section 10. The other visits (2, 4 and 5-month visits post treatment initiation) will be research-nurse visits, with a provider available to sign the next month's prescription.

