### **Serious Adverse Events (SAE) and unanticipated problems involving risk to subjects or others (UPIRSOs)**

An SAE is defined as any AE occurring at any dose that results in any of the following outcomes:

- death
- a life-threatening adverse experience
- inpatient hospitalization or prolongation of existing hospitalization++
- a persistent or significant disability/incapacity
- a congenital anomaly/birth defect

Other important medical events may also be considered an SAE when, based on appropriate medical judgment, they jeopardize the subject or require intervention to prevent one of the outcomes listed.

++ Note that hospitalizations for the following reasons should not be reported as serious adverse events:

- Routine treatment or monitoring of the studied indication, not associated with any deterioration in condition
- Elective or pre-planned treatment for a pre-existing condition that is unrelated to the indication under study and has not worsened since signing the informed consent
- Social reasons and respite care in the absence of any deterioration in the patient's general condition

- Note that treatment on an emergency outpatient basis that does not result in hospital admission and involves an event not fulfilling any of the definitions of a SAE given above is not a serious adverse event

Any serious or immediately life-threatening adverse experience, including those resulting in death, occurring while the subject is receiving study drug, or within 30 days of the subject's last dose of protocol therapy, regardless of the treating physician's opinion regarding drug relationship, will be reported by telephone and/or e-mail (within 24 hours of the event) to the Study PI and appropriate parties.

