#### **8.0 DEFINITION OF DOSE-LIMITING TOXICITY (DLT)**

DLT will be defined as any of the following events that are possibly, probably, or definitely attributable to imatinib.

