## **13.0 CRITERIA FOR REMOVAL FROM PROTOCOL THERAPY**

1. Adverse Events requiring removal from study
2. Refusal of further protocol therapy by patient/parent/guardian.
3. Non-compliance that in the opinion of the investigator does not allow for ongoing participation, including <70% of drug prescribed being taken. Compliance will not be contingent on completion of the pain journal as this not the primary endpoint of the study.
4. Physician determines continued protocol therapy is not in the patient's best interest.

Patients who are off protocol therapy are to be followed until they meet the criteria for Off Study (see below). Ongoing adverse events, or adverse events that emerge after the patient is removed from protocol therapy, but within 30 days of the last dose of investigational agent, must be followed and reported via RDE and AERS (if applicable). Follow-up data will be required unless consent is withdrawn.

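### The DLT accrual-halt rule counts patients with full follow-up, a term the plan never ties to a period, so the halt can come late or exceed the roughly 5% false-halt rate that the boundary implies

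*Combined protocol and SAP*

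**What the plan says.** Section 15.3 provides continuous monitoring of DLTs with a Pocock-type boundary for up to 20 patients. The count is compared with b_n out of n "patients with full follow-up (see table below"). On crossing, "enrollment will be halted, and a data safety meeting will be convened to determine whether or not the study should be continued". The boundary is described as a test, after each patient, that "the DLT rate is equal to 0.2, using a one-sided level 0.021430 test". The overall operating characteristic is left as template text: "probability of crossing the boundary at most [probability of early stopping".

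Section 8.0 defines the event by type and attribution only: "DLT will be defined as any of the following events that are possibly, probably, or definitely attributable to imatinib". It gives no period over which a DLT counts.

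Three other places offer a possible end of follow-up, but none is linked to Section 15.3:

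- Section 6.0: "Patients will receive Imatinib orally once daily for 6 months".
- The serious adverse event text in Section 7 covers events "occurring while the subject is receiving study drug, or within 30 days of the" last dose.
- Section 13.0: "Patients who are off protocol therapy are to be followed until they meet the criteria for Off Study". Section 14.0 sets that at 30 days after the last dose.

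**The concern.** This is the plan's only numerical study-level safety boundary. Crossing it pauses enrolment and convenes a meeting; it does not by itself stop the drug in treated patients. Its value therefore lies in limiting how many more patients start.

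Two readings of full follow-up pull in different directions.

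- **Fixed period.** Each patient counts after six months of drug plus 30 days, in enrolment order. The error rate holds, but a DLT reported within 24 hours under Section 7.0 waits until about month 7 from that patient's entry before it enters the rule.
- **Off study.** Each patient counts on reaching the Section 14.0 criterion. Patients who leave drug at a DLT then enter n ahead of DLT-free patients enrolled earlier. The early denominators are enriched for DLTs, and the implied error rate no longer holds.

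Two teams could apply the rule to the same data and act months apart.

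**Working it through.** **Inputs from the documents.** DLT rate 0.2, one-sided per-look level 0.021430 and a look after each patient (15.3); 20 treated patients (15.1); 6 months of drug (6.0); 30 days after last dose (14.0).

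**Assumed, because the documents do not give them.** Evenly spaced accrual at r = 0.5, 1 or 2 patients per month. DLT times either uniform over 6 months or early (exponential with mean 1 month, truncated at 6). Share of DLT patients who leave drug: 10%, 25% or 50%. Section 9.0 removes some DLT patients and lets others restart, so this share is unknown.

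**Step 1: reproduce the boundary.** b_n is the smallest k with P(Bin(n, 0.2) ≥ k) ≤ 0.021430. For example, at n = 3, P(≥3) = 0.008. At n = 6, P(≥4) = 0.01696 while P(≥3) = 0.09888. At n = 9, P(≥5) = 0.01958. For n = 3 to 20 this gives 3, 4, 4, 4, 5, 5, 5, 6, 6, 6, 7, 7, 7, 8, 8, 8, 9, 9. Any level from 0.019581 to just below 0.023278 gives the same boundary. The midpoint, 0.0214299, rounds to the stated 0.021430, so the plan's figure is reproduced.

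**Step 2: overall crossing probability.** An exact forward recursion over 20 patients gives 0.0484 at a DLT rate of 0.2, 0.552 at 0.4 and 0.834 at 0.5.

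**Step 3: fixed-period reading.** The earliest possible halt is when patient 3 completes, at month 2/r + 7, that is month 11, 9 or 8. By then 6, 10 or 17 patients are enrolled. To halt before the 20th entry, at month 19/r, patient n must satisfy (n − 1)/r + 7 < 19/r, so n − 1 < 19 − 7r. The last usable look is n = 16, 12 or 5. As a hand check at r = 2 and rate 0.5: the first three patients all have DLTs (0.125), or four of the first five do without that (3/32 = 0.09375), total 0.219.

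**Step 4: counting DLTs as they occur in enrolment order.** The crossing time is the time of the b_n-th DLT among the first n treated, minimised over n. Counting patients still in follow-up as no DLT so far can only undercount, so no trial crosses that would not cross on complete data. Any trial that crosses on complete data crosses here no later. The crossing probability is therefore unchanged.

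Results at a true DLT rate of 0.5, with means taken among trials that cross (200,000 simulated trials per setting):

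| | r = 0.5 | r = 1 | r = 2 |
|---|---|---|---|
| Mean enrolled at halt, fixed period | 11.8 | 15.3 | 19.4 |
| Mean enrolled at halt, as DLTs occur (early to uniform) | 9.1–10.0 | 9.6–11.8 | 10.8–15.2 |
| P(halt before 20th entry), fixed period | 0.752 | 0.663 | 0.219 |
| P(halt before 20th entry), as DLTs occur | 0.80–0.81 | 0.76–0.81 | 0.63–0.78 |

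At r = 2 the 0.219 becomes 0.359 if a look on the day of the 20th entry counts.

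**Step 5: off-study reading, crossing probability at a DLT rate of 0.2.** DLT patients who leave drug complete one month after the DLT, and all others at 7 months.

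| Share leaving | r = 0.5 | r = 1 | r = 2 |
|---|---|---|---|
| 10% | 0.050–0.052 | 0.052–0.056 | 0.057–0.064 |
| 25% | 0.053–0.056 | 0.059–0.068 | 0.072–0.097 |
| 50% | 0.057–0.063 | 0.071–0.092 | 0.107–0.179 |

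Some of these crossings come after enrolment is complete. Restricted to crossings before the 20th entry, the last cell is 0.075–0.152.

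**The case against.** The strongest reply is that the documents do give follow-up an end, that DLTs are acted on at once, and that the large figures depend on an accrual rate found nowhere in the plan.

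- **An end of follow-up exists.** True, in Sections 13.0 and 14.0. What is missing is the link to 15.3 and the order in which patients enter n, and these produce the two behaviours above.
- **Mitigation.** DLTs go to the principal investigator within 24 hours (7.0). There are weekly safety contacts in the first two months (6.0), individual holds and removals (9.0), and investigators may suspend at monthly review (18.1, 18.21). These soften a late halt. Suspension is discretionary, however, and does not replace a prespecified boundary.
- **Slow accrual.** At 0.5 per month the delay costs about two or three patients (11.8 against 9.1–10.0). This stands: the late halt is severe only with faster accrual.
- **False halts.** The off-study reading is an inference, the excess is small at a 10% leaving share, and a false crossing only pauses enrolment for a meeting. This also stands.
- **A short DLT period may have been meant.** With an illustrative one-month period, fixed-period counting halts at a mean of 8.9, 9.9 or 10.9 enrolled at rate 0.5, and the off-study crossing rate is 0.048–0.052 for leaving shares of 25–50%. The problem nearly disappears, but the plan states no such period.

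Three stronger readings are tempting and are not supported. A reader might infer that the plan breaches its own stated false-halt rate. It states none: 0.021430 is a per-look level and the overall field is blank. A reader might count every DLT at once over completers only, which gives about 0.22 or 0.42 at 1 or 2 patients per month (DLT times uniform over 7 months). The rule compares DLTs out of n patients, so nothing in it directs DLTs from outside those n into the count. Finally, the boundary row as read has 19 entries for 20 columns, and a reader might call it misprinted. Restoring one 5 at n = 9 reproduces every value, so this may be a loss in PDF reading.

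**Conclusion.** The concern holds as an undefined denominator with real consequences, and should be fixed. The boundary itself is sound: it follows from the stated test and implies 0.048 overall at a DLT rate of 0.2.

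Under the fixed-period reading that rate is kept, and the cost is delay, ranging from modest at 0.5 patients per month to a rule that seldom limits enrolment at 2 per month. Under the off-study reading the implied rate is exceeded, slightly in most settings. The value near 0.18 needs fast accrual, half of DLT patients leaving drug and early DLTs together. The boundary and the 0.048 are exact. The sizes of the delay and of the excess rest on assumed accrual, DLT timing and leaving shares, so they show a range and not the trial's operating characteristics.

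**What to change.** In Section 15.3:

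1. Replace the full follow-up condition. Apply b_n to the first n treated patients in enrolment order, cross as soon as the b_n-th DLT among them occurs, and count patients still in follow-up as having no DLT so far.
2. State the period over which a DLT counts.
3. State how patients who leave without a DLT are counted. There is a trade-off. With an assumed 10% leaving at a uniform time, counting them as DLT-free gives a false-halt rate of 0.038 but lowers crossing at a true rate of 0.5 from 0.834 to 0.777. Dropping them from n gives 0.055 and 0.840.
4. Fill the placeholder with the implied overall crossing probability, 0.048 at a DLT rate of 0.2.

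As a check only, compare the boundary row with the source table and correct it only if an entry is missing there.

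The cost is two or three sentences. No extra patients, visits or data are needed, because 24-hour DLT reporting is already required. The one statistical price is somewhat lower sensitivity if early leavers are counted as DLT-free.

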## **7.0 GRADING OF ADVERSE EVENTS**

An adverse event (AE) is defined as any unintended or abnormal clinical observation that is not of benefit to the patient. Either the condition was not present prior to exposure to test medication, or it has worsened in intensity or frequency following exposure to test medication. Adverse events will be graded according to the National Cancer Institute (NCI) Common Terminology Criteria v4.03 (CTCAE):

[http://ctep.cancer.gov/protocolDevelopment/electronic\\_applications/ctc.htm](http://ctep.cancer.gov/protocolDevelopment/electronic_applications/ctc.htm)

Any suspected or confirmed dose-limiting toxicity should be reported immediately (within 24 hours) to the principal investigator.

Principal investigators (PI) must report to the IRB as soon as possible, but in all cases within 5 working days from notification of any event that appears on the **List of Events that Require Prompt Reporting to the IU IRB**.

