### 18.21. Early Study Closure

At any time during the conduct of the trial, if it is the opinion of the investigators that the risks (or benefits) to the subject warrant early closure of the study, the Compliance Officer must be notified within 1 business day via email, and the IRB must be notified within 5 business days. Alternatively, the investigators may initiate suspension or early closure of the study based on their monthly reviews.

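### As supplied, the DLT boundary row in Section 15.3 is one entry short and, read left to right, contradicts the test it is said to equal

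*Combined protocol and SAP*

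**What the plan says.** Section 15.3 (Safety Monitoring) monitors DLTs continuously. Accrual halts when the DLT count reaches or exceeds b_n among n patients with full follow-up. On crossing, "a data safety meeting will be convened to determine whether or not the study should be continued".

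The table has columns n = 1 to 20. Its boundary row is two dashes followed by "3 4 4 4 5 5 6 6 6 7 7 7 8 8 8 9 9". That makes 2 + 17 = 19 entries, and the last cell is empty.

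The sentence under the table says that the boundary is equivalent to "testing the null hypothesis, after each patient, that the DLT rate is equal to 0.2, using a one-sided level 0.021430" test. The sentence above it says that the boundary "yields the probability of crossing the boundary at most [probability of early stopping] when the rate of dose-limiting toxicity" equals the acceptable rate; two bracketed template fields in that sentence have not been filled in.

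Three other provisions bear on the consequences:
- Section 6.0: "Patients will receive Imatinib orally once daily for 6 months".
- Section 7.0: "Any suspected or confirmed dose-limiting toxicity should be reported immediately (within 24 hours) to the principal investigator".
- Section 18.21: "the investigators may initiate suspension or early closure of the study based on their monthly reviews".

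**The concern.** The table and the sentence below it are meant to be two statements of one rule. Rate, level and look schedule fix the boundary completely, so the row can be recomputed, and as supplied it does not match. This is the only numerical safety stopping rule in the plan, and staff applying it would naturally read the table rather than recompute binomial tails.

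If the source carries the same row, the two statements give opposite answers at 5 DLTs in 9 patients, 6 in 12, 7 in 15 and 8 in 18. The stated test halts accrual and convenes the meeting; the table does not. At n = 20 the table gives no threshold.

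**Working it through.** **Inputs (Section 15.3).** Null DLT rate 0.2; one-sided level 0.021430; a look after each patient; halt if DLTs ≥ b_n.

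**Step 1. The boundary that the sentence defines.** b_n is the smallest k with P(X ≥ k) ≤ 0.021430, where X ~ Binomial(n, 0.2).

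| n | Test | Row, left to right |
|---|---|---|
| 1–2 | none | none |
| 3 | 3 | 3 |
| 4–6 | 4, 4, 4 | 4, 4, 4 |
| 7–9 | 5, 5, 5 | 5, 5, **6** |
| 10–12 | 6, 6, 6 | 6, 6, **7** |
| 13–15 | 7, 7, 7 | 7, 7, **8** |
| 16–18 | 8, 8, 8 | 8, 8, **9** |
| 19–20 | 9, 9 | 9, **blank** |

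**Step 2. Tails at the disputed looks, at rate 0.2.** P(X ≥ 5 | n = 9) = 0.01958; P(X ≥ 6 | 12) = 0.01941; P(X ≥ 7 | 15) = 0.01806; P(X ≥ 8 | 18) = 0.01628. All are below 0.02143, so the stated test halts at each. At n = 20, P(X ≥ 9) = 0.00998 and P(X ≥ 8) = 0.03214, so the test gives 9.

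**Step 3. Can rounding of the level explain the row?** No. A boundary of 4 at n = 6 needs a level of at least 0.01696. A boundary of 9 at n = 18 needs a level below 0.01628. No level satisfies both at rate 0.2. Normal-approximation, two-sided and mid-p versions of the test do not give the row either.

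**Step 4. Can one lost entry explain it?** Yes. I tried every single-entry insertion. Only an extra 5 at n = 7, 8 or 9 (all the same resulting row) makes the 20 looks agree. It moves each later entry one column right and puts 9 at n = 20.

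**Step 5. Is the stated level credible?** Yes. Any level from 0.01958144 (the tail for 5 of 9) up to just below 0.02327831 (the tail for 8 of 19) gives the full 20-value row. The midpoint is (0.01958144 + 0.02327831)/2 = 0.0214299, which rounds to the printed 0.021430.

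**Step 6. Size, if the source has this row and it is read left to right.** Exact recursion through n = 19:

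| True DLT rate | Stated test crosses | Supplied row crosses | Gap (points) |
|---|---|---|---|
| 0.2 | 4.8% | 3.7% | 1.1 |
| 0.3 | 22.5% | 18.3% | 4.1 |
| 0.4 | 53.3% | 47.2% | 6.0 |
| 0.5 | 81.5% | 77.3% | 4.2 |

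Gaps are taken from unrounded values. The largest is 6.0 points, at a rate of 0.40.

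**Step 7. Effect on accrual.** The documents give no accrual rate, so I assume L patients enrolled ahead of full follow-up. Expected accrual = Σ P(first crossing at n) × min(20, n + L) + 20 × P(no crossing). The supplied row minus the stated test gives these extra patients:

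| L (assumed) | Rate 0.3 | Rate 0.4 | Rate 0.5 |
|---|---|---|---|
| 0 | 0.37 | 0.64 | 0.64 |
| 5 | 0.16 | 0.31 | 0.37 |
| 11 or more | 0 | 0 | 0 |

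At L = 11 all 20 patients are already enrolled at the n = 9 look.

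**Step 8. The other alignment.** If the 19 entries are pushed one column right, they match the test at every look from n = 8 to 20. They differ only at n = 3 (none against 3), n = 4 (3 against 4) and n = 7 (4 against 5). That row crosses more often than the test through n = 20: 6.5% against 4.8% at rate 0.2, and 57.5% against 55.2% at rate 0.4.

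**The case against.** **The cell may never have been missing from the plan.** The text available here was read from a PDF, and other tables in it are visibly disordered, such as the CYP3A4 lists in Appendix B. A dropped repeat within a run of three 5s is the kind of loss that such reading can produce. This stands: the point is a conflict in the text as supplied, not a proven error in the plan.

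**The direction depends on alignment.** This also stands. Once a cell is lost, column positions are uncertain, and Step 8 shows that the other alignment makes the row stricter. The left-to-right reading is the one the supplied layout presents, with the last cell empty, but it is still an assumption.

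**The sentence below the table already gives a complete rule.** True, and it is why the row can be restored with confidence. It does not remove the conflict for someone who reads only the table.

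**The practical effect is modest.** Agreed. Crossing leads to a halt and a meeting. Looks wait for full follow-up on a 6-month treatment, so enrolment may run ahead of them. DLTs reach the principal investigator within 24 hours, and monthly reviews can suspend the study. With 20 treated patients in total (Section 15.1), no accrual is left to halt at n = 20.

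**Stronger readings that the documents do not support.**
- A reader might infer that the boundary was wrongly calculated. Steps 4 and 5 point the other way.
- A reader might take the chance that the stated test first crosses at a disputed look (21.2% at rate 0.4, 26.5% at 0.5) as the chance of missing a halt. It is not, because many of those paths cross the supplied row at a later look; the net loss is the gap in Step 6.
- A reader might treat the unfilled bracketed fields as leaving the rule undefined. Rate, level and looks already define it, so the blanks change no halt decision.

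**Conclusion.** The concern holds in a conditional form. As supplied, the row has 19 entries for 20 columns. Read left to right, it contradicts its defining sentence at n = 9, 12, 15 and 18 and gives nothing at n = 20. The arithmetic is exact and rests only on the stated rate, level and look schedule. The likely cause is one lost 5, with a sound design calculation behind it; whether it was lost in transcription or in reading the PDF cannot be settled from the documents.

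If the source table has this row, the table is more lenient than the stated test at four looks, by at most about 6 percentage points in crossing probability. The main consequence would be a later safety meeting, with on average well under one extra patient accrued. If the source table is complete, the point falls away.

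It is worth correcting because a decision threshold should not disagree with its own definition and the correction is cheap, not because the expected harm is large.

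**What to change.** Check the boundary row in the source document first.

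- **If it has the same 19 entries,** reconcile it with the stated test, whose row is: n = 1–2 none; 3: 3; 4–6: 4; 7–9: 5; 10–12: 6; 13–15: 7; 16–18: 8; 19–20: 9.
- **If it is complete,** leave the table as it is.

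As an editorial note only, the two bracketed fields in the same paragraph should be completed. The sentence under the table gives the rate as 0.2. The sponsor should supply its own intended cap on the crossing probability. For reference, the stated test crosses with probability 0.048 over 20 patients at rate 0.2; the plan does not state what cap was intended.

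Cost: one look at the source, at most one table row, and one sentence. No patients or procedures are affected.
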